Title: Optical Measurements of the Skin Surface to Infer Distinctions in Myofascial Tissue Stiffness

NCT number: NCT06390085

Date: February 3rd, 2023

Statistical Design and Power

Aim 1. We will evaluate the sensitivity of a suite of mechanical biomarkers. Using the imaging approach, we will create an optimal set of biomarkers which is the best classifier of myofascial pain state. In order to select the best suite of complementary metrics, which are most effective in predicting pain state, and which are simplest to accurate we will develop a classification strategy, we will perform multi-dimensional cluster analysis based on measured biomarkers. By using the biomarkers as predictors, data points representing different stimulus sets will be clustered into certain distinct groups based on the minimized average deviation (Jenks natural breaks classification method, 1-dimensional) and the minimized distance to the centroid (k-Means clustering, 2,3-dimensional). The match rate between clustered groups and ground-truth stimulus sets will determine the utility of unique biomarkers.

Aim 2. We will refine the requirements of the imaging deployment by evaluating tradeoffs in the array of ink speckles on the skin, in particular their density and heterogeneity requirements, to determine to what extent the density can be reduced yet still achieve similar imaging accuracy. We will perform ANOVA and t-tests with p values set at 0.5.

Sample size justification and power. Aim 1 will enroll 15 individuals. We will have a >80% power to identify biomarkers that have a moderate/strong rank correlation (e.g., Spearman's correlation ≥ 0.57) with pain. Aim 2 will enroll 6 individuals. These participants will be evaluated in refining requirements for imaging deployment, data collection, and data analysis.

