Will a recording device (e.g. audio, video, photographic) be used to collect data/materials from participants? Yes

What type(s) of recording device(s) will be used in this data tool? Video

Describe each recording device(s) and provide a justification for using the recording device.

We need the imaging information to capture the deformation patterns of the skin surface of the participant relative to the movements of the clinician's fingers. This is video data, taken at 30 - 100 frames per second. The recording devices is a raspberry PI camera, and we use three of them, aimed at the same point, so as to acquire 3D data from slightly distinct angles, so as to reconstruct the skin surface accurately. The exact model is a monocular camera (12 MP, Raspberry Pi High Quality, UK) with wide angle lenses (6 mm Vilros, Lakewood, NJ, USA) connected to microcontrollers (Raspberry Pi Zero W boards, UK).

Are the participant's identifying information included as part of the data at any time? No

How will you receive the data so that the data are not linked to identifying information?

A number will be assigned to each participant, starting at 1 and following. This number will be added to the signed consent forms. These forms will be stored as noted above. Any data linking identifying information will be stored securely and separately from the imaging data.

Data Source Name: Verbal pre and post pain assessment

When will the data be collected? Data will be collected after IRB-SBS approval of this protocol.

Who will collect the data? Primary data source

Describe this Data Source.

Pain levels of the participant at the point of each manual assessment, i.e., before and after the massage intervention. These are to be taken bilaterally. We will associate this data with the imaging data to determine if the level of pain is associated with mechanical deformation cues we observe, e.g., amount of skin strain.

Will a recording device (e.g. audio, video, photographic) be used to collect data/materials from participants? No

Are the participant's identifying information included as part of the data at any time? No

How will you receive the data so that the data are not linked to identifying information?

We will obtain these verbally and store them in a spreadsheet using the numerical identifier for that patient, and stored in a file structure/directory of the same number.

Associate Data Sources with Data Sources

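### The SAP's only power figure is for a Spearman correlation that it never specifies as an analysis, while Aim 1 is decided by a cluster match rate with no chance level, error rate or precision

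*SAP*

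**What the plan says.** In the SAP, under Statistical Design and Power, Aim 1 seeks the set of biomarkers that classifies pain state best. The method is clustering: "we will perform multi-dimensional cluster analysis based on measured biomarkers", with Jenks breaks in one dimension and k-means in two or three. The decision criterion follows: "The match rate between clustered groups and ground-truth stimulus sets will determine the utility of unique biomarkers". Neither the Aim 1 nor the Aim 2 text names a correlation.

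The sample size paragraph rests on something else. "Aim 1 will enroll 15 individuals", and then "We will have a >80% power to identify biomarkers that have a moderate/strong rank correlation", illustrated as "Spearman's correlation ≥ 0.57) with pain". No alpha accompanies this. The only significance threshold in the SAP is 0.5, and it belongs to the Aim 2 ANOVA and t-tests. No power or precision is given for the match rate.

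The Protocol, Data Sources, on the verbal pre and post pain assessment, adds an intention: "We will associate this data with the imaging data to determine if the level of pain is associated with mechanical deformation cues". It says that pain is taken before and after the massage and on both sides. It does not say how the association will be tested.

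**The concern.** The power sentence speaks of identifying biomarkers, which is the job that Aim 1 gives to the match rate. A reader will therefore credit the biomarker selection with more than 80% power, although that figure concerns a different quantity. A correlation test has a null value and an error rate. The match rate, as written, has no threshold, chance level or error rate, so nothing says what value would count as evidence. The protocol wants these data to support a later grant application. If the choice between a correlation and a match rate is left until results are known, whichever looks better can be reported.

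**Working it through.** **Step 1. Which analysis the power belongs to.**

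| Place | Quantity | Test, alpha or threshold |
|---|---|---|
| SAP, Aim 1 | Match rate from Jenks or k-means | None |
| SAP, Aim 2 | ANOVA and t-tests on speckle requirements | Threshold 0.5, no power |
| SAP, sample size | Spearman of at least 0.57 with pain, N=15, power above 80% | No alpha |
| Protocol, Data Sources | Pain related to deformation | No test, alpha, side or time point |

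The powered quantity appears in neither SAP analysis paragraph.

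**Step 2. Can the stated figure be reproduced for its own test?** Inputs from the SAP are rho = 0.57 and n = 15. Alpha = 0.05 is an assumption.

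Power = Φ(atanh(rho) × √((n − 3)/v) − z), where v is the variance factor: 1 (Pearson), 1.06 (Fieller) or 1 + rho²/2 = 1.162 (Bonett–Wright).

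- atanh(0.57) = 0.6475.
- Two-sided, v = 1: 0.6475 × √12 − 1.960 = 2.243 − 1.960 = 0.283, power 61.1%.
- Two-sided, v = 1.06: 2.179 − 1.960 = 0.219, power 58.7%.
- Two-sided, v = 1.162: 2.080 − 1.960 = 0.120, power 54.8%.
- One-sided: 72.5%, 70.3% and 66.8% in the same order.
- Simulation of the Spearman test (bivariate normal, true Spearman 0.57, 40,000 replicates): 59.7% two-sided, 71.6% one-sided.

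So the figure is not reproduced at 0.05. What would reproduce it:

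- A larger N. From n = 3 + v × ((1.960 + 0.842)/0.6475)², 80% two-sided power needs 22, 23 or 25 people for the three values of v. One-sided it needs 18 to 21. At the protocol's N=30, two-sided power is 88–92% by formula and 91% by simulation.
- A looser alpha. At N=15, two-sided alpha 0.2 gives 79–83%, and 0.5 gives 92–94%.

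**Step 3. Can the figure be carried over to the match rate?** The SAP gives no number of clusters, group sizes or points per person, so this step is an illustration only. It assumes three clusters (the protocol has three groups), five people per group (15/3) and one point per person.

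- Pure-noise 2-D k-means with best-label matching: the mean match is about 50%. With 15 points the rate moves in fifteenths. About 18% of null runs reach 60% (9/15) and about 5% reach 67% (10/15), so the 95th percentile is about 60–67%.
- Precision of an observed 67% match, treating points as independent: 1.96 × √(0.67 × 0.33/15) = 0.24, or 24 points. At 30 it is 17 points.
- One normal biomarker, equally spaced group means, Jenks with three classes: where the Spearman correlation with group is about 0.55–0.60, a match-rate test at no more than the 5% level has power of about 23–28% with best-label matching, or 37–45% with labels fixed by order.

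On these assumptions the match rate falls well short of 80% at an effect near the one the SAP names.

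**The case against.** The strongest reply is that the correlation is planned after all. The protocol intends to relate pain to deformation, and a rank correlation would serve that naturally. The power sentence itself names the coefficient, the two variables, the effect size and the purpose. One could read the plan as screening by correlation and then clustering the survivors. That reading is open, but neither document states the sequence, and the SAP still lets the match rate alone determine utility.

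This reply does defeat a stronger reading. A reader might infer that the stated power belongs to no planned analysis, or that the correlation will never be run. The documents do not support that. They show a planned association without a named test.

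Three further cautions stand.

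- The gap between 60% and 80% is a separate fault in the power statement. It would remain if Spearman were the declared primary test, so it does not measure the mismatch. It also depends on an alpha that the SAP does not give.
- The match-rate figures depend on the assumed layout. Assessment on two sides and at two times could give four points per person, or 60 points at N=15. The naive half-width is then 1.96 × √(0.67 × 0.33/60) = 12 points, and wider once within-person correlation is allowed for.
- It might be inferred that clustering should become merely descriptive. The aim is to find the best classifier, so that step would work against it and is not needed.

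**Conclusion.** The point holds in this form: the SAP's only power figure is for a test that the SAP does not specify, and it does not describe the match rate that decides Aim 1. This can be read from the text and needs no assumption.

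The sizes do rest on assumptions. At an assumed alpha of 0.05, power for the correlation at N=15 is about 60% two-sided or 72% one-sided, so the claim of more than 80% is not met; at N=30 it is met, at about 91% two-sided. Which N applies is itself unsettled: the SAP gives 15 for Aim 1, while the protocol overview gives 30. The 50% chance match and its 60–67% upper tail show why an unreferenced match rate is hard to interpret. They are not estimates for this study.

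**What to change.** Change SAP Aim 1 and the sample size paragraph as follows, before any results are seen.

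1. Add to Aim 1 the Spearman correlation of each biomarker with the verbal pain rating. Use one pre-massage value per participant, with a stated rule for which side is used. Set two-sided alpha at 0.05, report a confidence interval, and state a multiplicity rule across biomarkers.
2. Restate the power of that test at the N that will be analysed, after reconciling the SAP and protocol numbers. Say plainly that this power does not apply to the match rate.
3. Keep the match rate as the classifier criterion, but judge it against a permutation chance level, permuting by participant so that repeated points from one person stay together. Report it with a confidence interval.

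The cost is SAP wording and slightly more analysis work; no procedure or measurement is added. The stated power becomes less favourable if N stays at 15, and a multiplicity adjustment would lower it further.

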What is the relationship between the participants of this study, and the Principal Investigator, Faculty Sponsor, and the Research Team (Sub-Investigators)? Does the Principal Investigator, Faculty Sponsor, or the Research Team (Sub-Investigators) know any of the participants personally or hold any position of authority over the participants (including but not limited to: grading authority, professional authority, etc.)? Do any of the researchers listed on the protocol stand to gain financially from any aspect of this research?

There are no relationships as described above.

Note that the PI will not carry out any participant studies, or have direct access to any identifying information. Therefore, students enrolled in courses taught by the faculty advisor will not be restricted from participation.

Additionally, the participants will not be known beforehand, and no researchers stand to gain anything financially from this research.

Recruitment & Consent

How will participants be approached or contacted for recruitment into the study?

We will contact participants through an email advertisement through the University of Virginia's College of Engineering. There will be no recruitment involving any courses taught by the PI. Upon a participant contacting us, we will follow-up by email to give them the Screening Question, via Qualtrics. This is done to determine who to invite to the study, as we are attempting to acquire roughly equal numbers of participants in the three groups.

If a potential participant does not qualify to be in the study, because, for example, we have too many "normal" participants. We will respond to let them know that they do not qualify. Otherwise, we will let them know that they do qualify and begin to schedule a day and time to participate.

Do participants have any limitations on their ability to consent ? No

Describe the limitations on their ability to consent:

What are the consent processes for this study?

We will have a consent form for participants to sign directly before the experiment. The consent form will be presented by the study proctor. All participants will be able and willing to provide and document their consent.

Students currently taking any course the PI is teaching will not be eligible until completion of the course final (December 7, 2023).

Will participants be deceived and/or have information withheld from them about the study? No

Will participants be debriefed? No

Recruitment & Consent Tools

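### SAP Aim 1 selects a biomarker set by its match rate but plans no chance reference or out-of-sample score, so the selected set's rate is expected to be optimistic

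*SAP*

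**What the plan says.** SAP, Aim 1, sets a selection goal: "we will create an optimal set of biomarkers which is the best classifier of myofascial pain state". The method is clustering: "By using the biomarkers as predictors, data points representing different stimulus sets will be clustered into certain distinct groups", by Jenks natural breaks in one dimension and k-means in two and three. The criterion is: "The match rate between clustered groups and ground-truth stimulus sets will determine the utility of unique biomarkers".

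SAP, Sample size justification and power, says "Aim 1 will enroll 15 individuals" and claims more than 80% power to "identify biomarkers that have a moderate/strong rank correlation" (Spearman 0.57 or more) with pain. The six Aim 2 participants are assigned to imaging requirements, not to checking the set chosen in Aim 1.

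The Protocol describes three groups (Active, Latent, Normal) and screens for balance, "as we are attempting to acquire roughly equal numbers of participants in the three groups" (Recruitment & Consent). The study overview gives 30 participants; Participant Groups gives 15 in each of three groups, which makes 45. Both sides are assessed before and after massage, so one person can supply up to four points.

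Neither document states the number of clusters k, the candidate biomarkers, the rule that maps clusters to labels, what the stimulus sets are, or whether a data point is a person, a side or a time. Neither describes a chance reference, cross-validation or held-out data.

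**The concern.** The largest of several noisy match rates overstates the rate that the chosen set would reach in new people. If clusters are also named after the fact, by whichever assignment agrees best with the labels, each rate is pushed up before any selection. The clustering itself does not use the labels, but the labels enter at both of these later steps. That the same participants choose the set and supply its rate is inferred: no other sample is described.

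No treatment decision depends on Aim 1. But the Protocol's opening summary says the data should support a larger grant application, and the match rate is the only stated measure of a biomarker's utility. A rate of 60% to 67% looks good beside a nominal 33%. The question is how often noise alone would produce it.

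**Working it through.** **The plan's own figure.** The SAP states no expected or target match rate. Its only Aim 1 figure is the power for a rank correlation. By Fisher's z at two-sided 5%, power = Φ(atanh(0.57)·√((15−3)/c) − 1.96). With c = 1 this is Φ(0.648 × 3.464 − 1.96) = 61%; with c = 1 + 0.57²/2 = 1.162 it is 55%. So the stated figure of more than 80% is not reproduced at that level. That is a separate matter, and it says nothing about match rates.

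**Inputs.** From the documents: N = 15 (SAP), 30 or 45 (Protocol); one to four points per person. Assumed: k = 3 with equal groups (the Protocol's three groups); three candidates (the Protocol's summary names lateral mobility, compression and distraction), giving 3 + 3 + 1 = 7 sets; within-person correlation 0.5 where there are four points; independent normal noise.

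**Formula.** Let M(i, j) count the points in cluster i with label j. The match rate is the maximum, over the 6 assignments π of clusters to labels, of Σ M(i, π(i)) / n. The selected set is the one with the largest match rate.

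**Reference case.** For one prespecified biomarker with a fixed cluster order, the expected rate under noise is Σ P(cluster i) × 1/3 = 33%. Simulation gives 33% at every N, so there is no bias.

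**Pure noise, best relabelling, mean match rate.**

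| People × points | One biomarker | Best of 3 single | Best of 7 sets |
|---|---|---|---|
| 15 × 1 | 50% | 56% | 59% |
| 30 × 1 | 45% | 49% | 51% |
| 45 × 1 | 43% | 46% | 48% |
| 15 × 4 | 44% | not given | 51% |
| 30 × 4 | 41% | 44% | 46% |
| 45 × 4 | 40% | 42% | 43% |

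**How often the best noise set reaches a given rate.**
- 15 × 1: 60% (9 of 15) in 59% of studies; 67% (10 of 15) in 21%, with repeat runs up to about 24%; 73% in 5%; 80% in 0.9%.
- 30 × 1: 50% in 73% of studies; 60% in 7%.
- 15 × 4: 50% in 61% of studies; 60% in 6%.
- 30 × 4: 50% in 12% of studies; 55% in about 1%.

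**With a real signal** (one biomarker shifts by 1 SD between adjacent groups):
- 15 × 1: the selected set averages 66%, against 59% for noise. In a run that also scored new participants, noise gave 59.3% apparent and 33.4% in new people (optimism 25.9 points); the signal gave 67.0% and 48.5% (18.5 points).
- 30 × 4: the selected set averages 60% and reaches 55% in 87% of studies.

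**Other assumptions.**
- 15 × 1, more candidates: 6 candidates (6 + 15 + 20 = 41 sets) give 65% under noise; 10 candidates (10 + 45 + 120 = 175 sets) give 70%.
- 15 × 1, candidates correlated 0.8: 57% for the best of 7.
- Fixed cluster order, best of three single biomarkers: 43% (15 × 1), 41% (30 × 1), 40% (15 × 4), 38% (30 × 4). Selection alone therefore lifts the rate above 33%.
- Label before/after instead (k = 2, nominal 50%): best of 7 is 61% at 15 × 2, and 58% at 30 × 2 or 15 × 4.

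**The case against.** The strongest reply has three parts.

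First, the criterion can be read as a ranking device. The SAP does not say that the winning rate will be reported as accuracy in new people, and ranking suffers less from optimism. With the 1 SD signal in one of three candidates, the informative biomarker ranked first among the single biomarkers in 70% of studies at 15 × 1, 88% at 30 × 1, 92% at 15 × 4 and 99.8% at 30 × 4, against 33% by chance. This stands: the point concerns the reported rate and its interpretation, and is not a claim that selection fails.

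Second, a reader might infer that moderate match rates can never be told from noise. The documents do not support that. With the Protocol's 30 participants and four assessments each, 55% would be informative: about 1% of studies under noise against 87% with the signal. The overlap is serious at 15 people with one point each. But the 55% is recognisable as informative only once a chance level has been computed, and none is planned.

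Third, the size rests on inputs that the SAP does not give, and the stimulus sets may not be the three pain groups. This also stands. Bias is not automatic: one prespecified biomarker with a fixed cluster order has none. But the SAP does not plan that. It sets out to choose the best suite across one, two and three dimensions: "In order to select the best suite of complementary metrics, which are most effective in predicting pain state".

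The planned pain association does not answer the point. The Protocol says "We will associate this data with the imaging data to determine if the level of pain is associated with mechanical deformation cues we observe", and the SAP has its power statement, but neither says that this analysis selects the set or calibrates the match rate.

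**Conclusion.** The concern holds in conditional form. Choosing the best of several sets by match rate, with no chance reference or out-of-sample score, makes the selected set's rate optimistic; matching clusters to labels after the fact adds to this. Confidence in the direction is high. The size is illustrative and depends on k = 3, equal groups, three candidates, best relabelling and the choice of data point. Under those assumptions the selected noise set averages 43% to 59% across the sample sizes and points per person examined, not 33%. At the SAP's 15 people with one point each, a rate of 60% to 67% is ordinary under noise; a rate of 80% would still stand out. It would go too far to conclude that Aim 1 cannot identify useful biomarkers or that every moderate rate is uninterpretable. This is a cheap improvement to a pilot.

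**What to change.** **Main change, in SAP Aim 1.** Judge each match rate, and the selected set, against a permutation null. Permute group labels between participants, keep all sides and times of a participant together, and repeat the whole selection and cluster-to-label matching in every permutation. If the label is before/after, swap it within participant instead. To make this possible, fix in advance the reference label, k, the candidate biomarkers, the data point and the mapping rule. Jenks and k-means can stay.

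The unit of permutation matters. At 15 × 4 with correlation 0.5, a nominal 5% test rejected pure noise in 4% of simulated studies when participants were permuted, but in 34% when single points were.

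**Optional secondary.** Report cross-validated accuracy with whole participants held out and the selection and mapping repeated in each training fold. State that it is imprecise: under noise at 15 × 1 it averages 33%, but the central 95% of studies run from 7% to 67%.

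**Cost.** SAP wording and a little programming; no new data. The reported result will look less favourable. With one point per person, permutation power at 15 people is about 18% for a 1 SD step and 76% for 2 SD (54% and over 99% at 30 people).

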About half the U.S. adult population suffers from chronic neuromusculoskeletal pain. While its evaluation and treatment are often addressed using soft tissue manipulation (STM), its efficacy is mostly based upon clinician judgement. Robust biomarkers are needed to quantify the effects of STM on patient outcomes. Among noninvasive methods to quantify the mechanics of myofascial tissue, most are limited to small (<10 mm 2), localized regions of interest. In contrast, we propose to develop an approach to optically measure a larger (~ 100 cm 2) field of deformation at the skin surface simultaneously as force is applied. We will derive biomarkers based on skin lateral mobility, compression, and distraction to infer distinctions in myofascial tissue stiffness. Specifically, we will deploy multiple cameras to track ink speckles whose fields of stretch deformation are resolved with digital image correlation. A preliminary system has been developed and evaluated in differentiating bilateral distinctions of the cervicothoracic region in a small group of participants, as a licensed clinician performs STM. These preliminary results indicate that the optically derived surface biomarkers can differentiate bilateral differences in skin mobility, with trend directions in deformation similar to measurements with an instrumented force probe. These findings suggest skin surface measurements are capable of inferring underlying myofascial tissue stiffness, although further confirmation requires a larger, more diverse group of participants. With the preliminary ability to differentiate tissue bilaterally, our next step is to collect sufficient data to prove we can differentiate tissue changes before and after STM intervention, in a larger cohort of participants, and refine system engineering requirements to apply for an NIH R21 or R01 award.

What will participants do in this study? Please provide an overall summary of the study plan. Where and when it will be conducted? What do you hope to learn from these activities? If the study has more than one phase, clearly map out the different phases. You will be required to describe the study components in more detail in later sections but use this paragraph to help your IRB reviewer to understand the general outline of the study. Other sections in the protocol form can be seen below.

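### SAP Aim 1 ranks biomarker sets on raw match rate and aims to name a best one, with no check that the candidates differ by more than chance

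*SAP*

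**What the plan says.** Under Aim 1 (SAP, Statistical Design and Power), the stated goal is that "we will create an optimal set of biomarkers which is the best classifier of myofascial pain state". Candidates are clustered by Jenks natural breaks in one dimension and by k-means in two or three. They are then judged on agreement with the known groups: "The match rate between clustered groups and ground-truth stimulus sets will determine the utility of unique biomarkers". The same paragraph also says that the chosen metrics should complement one another and be simple, but it does not say how either quality is weighed against the match rate.

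On size, the SAP says "Aim 1 will enroll 15 individuals". The protocol's study overview gives 30 participants, and its Participant Groups section lists 15 in each of three groups, which makes 45. The only precision statement for Aim 1 is "We will have a >80% power to identify biomarkers" that have a "moderate/strong rank correlation (e.g., Spearman's correlation ≥ 0.57) with pain". The ANOVA and t-tests belong to Aim 2. Neither document gives an interval, a paired comparison, a minimum difference or a tie rule for match rates.

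**The concern.** All candidate sets are scored on the same few people. Their match rates are therefore paired, coarse and imprecise. Some set always comes out highest, so a rule that follows the raw rate will name a leader whether or not the data can separate it from its rivals. A better biomarker could then be set aside because one or two people were placed differently.

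This is a separate problem from optimism in the match rate. Cross-validated or otherwise unbiased rates would still be ranked partly by chance at this size. What is at stake is what Aim 1 may conclude: a report that calls one set the best classifier would claim more than the data show.

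**Working it through.** **Inputs.** From the documents: N = 15 (SAP), 30 or 45 (protocol); three groups of roughly equal size; ranking by match rate. Assumed, because the documents are silent: true match rates, number of candidate sets, correlation between biomarkers, one classified value per person, and a two-sided 5% level for Aim 1.

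**1. The plan's own figure.** Power for a correlation of 0.57 by Fisher's z is Φ(atanh(0.57) × √(N − 3) − z). At N = 15, 0.6475 × √12 = 2.243. Two-sided 5% gives Φ(2.243 − 1.960) = 61%; one-sided 5% gives Φ(2.243 − 1.645) = 73%. The stated power above 80% is not reproduced at N = 15 with either level; N = 30 gives Φ(3.365 − 1.960) = 92%. That is a separate issue. For this point, what matters is that the figure concerns correlation with pain and does not show whether one set classifies better than another.

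**2. Smallest separable margin.** If all m discordant people favour one set, the exact McNemar p-value is 2 × 0.5^m.
- 5-0: 2/32 = 0.063.
- 6-0: 2/64 = 0.031.
- With discordance both ways the net margin must be larger: 7-1 gives 2 × 9/256 = 0.070, and 8-1 gives 2 × 10/512 = 0.039.

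The minimum net margin is therefore 6 people: 6/15 = 40 points, 6/30 = 20 points, 6/45 = 13 points.

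**3. Precision of one rate, and paired power.** A rate of 10/15 (67%) has an exact 95% interval of 38% to 88%. At N = 15, exact paired power is about 1-3% for 70% against 60%, and about 6-10% for 80% against 60%, with within-person correlation from 0 to 0.6.

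**4. How often an inferior biomarker scores strictly highest.** Take one better biomarker with correct count X ~ Bin(N, p₁), and k − 1 independent rivals with counts Bin(N, p₂) and distribution function F. The chance is Σₓ P(X = x) × [1 − F(x)^(k−1)]. A second check simulated three-class natural breaks with equal groups and group steps of 1.5 SD against 1.0 SD, which gives mean match rates of about 67% and 57%.

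| N | Candidates | Binomial, 70% v 60% | Simulated natural breaks |
|---|---|---|---|
| 15 | 2 | 22% | 21-22% |
| 15 | 3 | 34% | 30-33% |
| 15 | 5 | 47-48% | 44-48% |
| 30 | 3 | 27% | 26-27% |
| 30 | 5 | 39% | 36-40% |
| 45 | 3 | 22% | 19-21% |
| 45 | 5 | 33% | 28-32% |

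At N = 15 with 3 or 5 candidates, the better biomarker ties for top in roughly a further 14-19% of studies, and the SAP does not say what happens then.

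**5. Sensitivity.** For 80% against 60% at N = 15 the chance is about 8% with two candidates, 13% with three and 21% with five. With biomarkers correlated at 0.6 in the natural-breaks model, the N = 15 figures for 3 and 5 candidates fall to about 27% and 38%.

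**The case against.** The strongest reply is that this is a small, single-day pilot with no treatment decision resting on the ranking, and that the SAP seeks a complementary suite and not strictly one winner. Part of this stands. Match rate is not the only quality that the SAP names, and a pilot may rank candidates without testing them. But the SAP also speaks of an optimal set that is the best classifier, and match rate is the only one of its criteria with a stated measure.

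Four stronger readings are tempting, and the documents do not support them.

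- *A wrong biomarker wins in a third to a half of studies.* That range needs about 3 to 5 independent candidates some 10 points apart at N = 15. The documents give no true rates, number of candidates or correlation. The protocol names three kinds of biomarker (lateral mobility, compression, distraction), and one-, two- and three-way combinations of three metrics would give 3 + 3 + 1 = 7 sets. These overlap and come from the same skin-deformation measurement, so independence is doubtful.
- *Match rates move in steps of 1/15 and a simple McNemar test applies.* This needs one value per person. The SAP clusters data points, and the protocol's assessments are on both sides, before and after massage, so up to four correlated points per person are possible.
- *The chosen set goes straight into the next grant.* The protocol's stated next step is to "refine system engineering requirements to apply for an NIH R21 or R01 award", which is closer to Aim 2.
- *When sets cannot be separated, carry forward the simplest.* At N = 15 almost nothing can be separated, so simplicity would make the choice. In simulation with simplicity unrelated to quality, that rule carried forward an inferior biomarker in about 68-79% of runs, against 41-55% for ranking by raw match rate.

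**Conclusion.** The point holds in limited form. The SAP lets raw match rate decide utility and aims at a best classifier, without any measure of whether candidates differ. The minimum separable margin (40, 20 or 13 points at N = 15, 30 or 45) follows from exact arithmetic and needs only one value per person and a two-sided 5% level.

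The chance of a wrong leader is conditional. At assumed true rates of about 67% and 57% with independent biomarkers, it is about 22%, 33% and 44-48% at N = 15 for 2, 3 and 5 candidates, and about 20-32% at N = 45 for 3 to 5. Settling the conflict over sample size in favour of a larger number would reduce the problem but not remove it. The defect limits what Aim 1 may claim; it does not invalidate the study, and ranking by match rate remains a reasonable way to order candidates.

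**What to change.** Add the following to the SAP under Aim 1.

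- State the unit that is classified, and how many points each person contributes.
- For the top-ranked set against each competitor, report the paired difference in match rate with a bootstrap interval that resamples people, keeping all their sides and pre/post points together. Use exact McNemar only if there is one value per person, and then let it decide. At N = 15 a percentile bootstrap can be too generous: with classifications held fixed, a 4-0 split leaves a (11/15)^15 = 0.0095 chance of a zero difference, so a 95% interval excludes zero although the exact p-value is 2/16 = 0.125.
- Still rank by match rate, but report every set not distinguishable from the top as a candidate.
- Claim a single best classifier only if its paired interval against every rival excludes zero.
- Use the SAP's simplicity criterion only to break exact ties in match rate, not to choose by default within the indistinguishable group.

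The cost is a few sentences and minor computation on data already planned. The downside is that, at this size, Aim 1 will usually report several candidate sets instead of one proven best.
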